### **Patient Sampling**

The RA will screen patients using convenience sampling methodology.

### **Patient recruitment, enrollment, and progress through the study**

Once a patient is screened and determined to be eligible, the RA will review the patient's ED electronic health record (dashboard or face sheet) and record (on a redcap database) the following de-identified information: race/ethnicity, gender, ESI level, insurance status, and chief complaints. [Please see data collection form/survey for further details collected.]

Collecting de-identified data from patient's charts poses no or minimal risk to the patient and it is generally considered acceptable to do this without previously consenting patients. We will keep this information on all patients, even if they refuse to participate in the survey portion, as this information is helpful to understand who are the patients that refused to participate in the study and who are the patients who did participate in the study to comment on the potential sampling bias. These demographic data are (a) de-identified, (b) readily available, (c) can be collected as a chart review without individual patient consent, (d) are not sensitive information, and (e) for patients who do not want to participate in the survey, are not linked in any way with the study questions. The information collected allows the investigators to compare the demographics of participants and non-participants; and therefore, to ensure that the sample is not biased.

If a patient meets the inclusion criteria, a RA will administer the consent for collection of their name, medical record number, and survey responses.

### **D. DATA ANALYSIS**

We will collect the following data: Age, Gender, Race, Ethnicity, State of residence, parental age, parental education level, household income, insurance status, parental report of immunization status and the reason for under-immunization if applicable. The sub-investigators will perform the data analysis at Albany Medical Center (AMC) with an AMC approved password protected PC. Storage of files will be on a password protected departmental drive. Use of a password protected master key document to store identifiers separately from other study variables, which will be collected and stored through REDCAPs.

Our primary outcome is the demographic variables and immunization beliefs that are associated with RSV under-immunization. Survey responses will be used to stratify outcomes according to child's age, Gender, Race, Ethnicity, State of residence, parental age, parental education level, household income, insurance status, and sources of health information. The secondary outcome is the improvement in immunization confidence (defined as converting from "definitely not intent, unsure about intent, or probably not intent" to "intent") stratified by patient-centered immunization messaging.

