## B. STUDY DESIGN

This will be a cross sectional RCT study conducted through web-based surveys to determine factors and facilitators contributing to measles immunization confidence in the ED.

*Aim 1: Identify the characteristics of the measles under-immunized population.* Parents of patients aged 1 year up to and including 6 years of age who present to the AMC pediatric ED between 6/1/2025 and 6/1/2026 will be screened for the below exclusion criteria:

- The patient is critically ill- Any life-threatening condition that requires pharmacological and/or mechanical support of vital organ functions, i.e. shock, moderate to severe asthma exacerbation, airway obstruction, anaphylaxis, etc.
- The patient presents with major (i.e. leveled) trauma
- The patient presents with concern for physical or sexual assault
- The patient presents with need for child protective service evaluation
- The patient or guardian are not English speaking
- The patient presents in custody of a juvenile detention center or law enforcement
- The patient presents without a consenting parent or legal guardian present at time of evaluation

Parents of children meeting the above inclusion and exclusion criteria will be approached for consent to participate in the study by convenience sampling weekdays 0900-1700. All consenting guardians will complete a brief survey to assess parental demographics and child immunization history. The below questions will be included in the brief survey:

- Age of caregiver
- Age of child
- Race of caregiver
- Ethnicity of caregiver
- Education level of caregiver
  - High school degree
  - College/University/technical school degree
  - Post-graduate college/university degree
- Household income level of caregiver
  - <24,000
  - 24,001-53,000
  - 53,001-89,000
  - 89,001-136,000
  - ≥136,001
  - Unknown
- What source do you find to be the most effective at communicating vaccine information
  - Social media
  - PCP (Primary care physician)

- Personal communication with friends/families
- Government agencies (i.e. Center for Disease Control and Prevention)
- Pharmaceutical companies
- On average, how many minutes do you (the guardian) spend on social media outlets per day?
  - 0-30 minutes
  - 31-60 minutes
  - 61-120 minutes
  - 121-180 minutes
  - 181-240 minutes
  - ≥241 minutes
- Is your child up to date with all routine (Not including influenza, COVID-19, RSV) immunizations at this time?
- Is your child immunized against Influenza for this season?

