- Is your child immunized against COVID-19 for this season?
- Is your child immunized against RSV for this season?
  - Yes, the mother was immunized for RSV during pregnancy.
  - Yes, the child was immunized for RSV as an infant.
  - No
  - Unsure

All participants who identify that their child is under-immunized for measles (i.e. did not receive 1st MMR immunization at 1 year of age OR 2nd MMR immunization at 4 years of age) will go on to complete a comprehensive survey to assess immunization beliefs, to include:

- Please indicate that you agree or disagree with the below statements when thinking about getting your child up to date with all of their recommended immunizations?
  - Receiving all the recommended vaccines would significantly reduce my child's risk of getting sick (Vaccine Efficacy)
    - Agree or Disagree
  - Receiving all the recommended vaccines would be safe for my child (Vaccine Safety)
    - Agree or Disagree
  - Receiving all the recommended vaccines would be like performing an experiment on them (Vaccine Distrust)
    - Agree or Disagree
  - Receiving all the recommended vaccine will lead to long-term health problems for my child (Vaccine Long-Term Health Problems)
    - Agree or Disagree
  - Receiving all the recommended vaccines would be harmful to my child because of their current medical condition (Child's Medical Condition)
    - Agree or Disagree

- Agree or Disagree
- Receiving all the recommended vaccines is unnecessary because there is less risk now that young children will be infected with the virus or bacteria (Low Risk of Infection)
  - Agree or Disagree
- Receiving all the recommended vaccines is unnecessary because America has reached herd immunity for the virus or bacteria (low risk for infection)
  - Agree or Disagree
- The opinion of my child's doctor or healthcare provider will influence my decision about getting my young child vaccinated (Not recommended by Provider)
  - Agree or Disagree
- Getting children vaccinated against infectious diseases supports the community by stopping the spread of the disease among other children and adults (Stopping Community Spread)
  - Agree or Disagree
- I do not have enough information about all the recommended vaccines to be comfortable giving them to my child (lack of information)
  - Agree or Disagree
- I do not have a health care provider who has offered my child the vaccine (lack of healthcare access)
  - Agree or Disagree

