- I cannot miss work (have my child miss school) for a doctor's appointment to receive the vaccine (Social barriers)
  - Agree or Disagree
- I do not have transportation to get my child to the doctor's appointment to receive the vaccine (social barriers)
  - Agree or Disagree

– “Do you plan to get your child fully immunized for measles?”

- “Definitely not”
  - “Probably not”
  - “Unsure”
  - “Yes”

*Aim 2: Explore the impact of favorable immunization messaging on parental confidence in the measles in the under-immunized population.*

All guardians who complete the comprehensive survey will be randomized to receive one of four patient-centered immunization messages. The guardian will then be asked again if they plan to immunize their child against RSV this season and if they would accept the immunization if we administer it at the current visit.

- “Would you give your child the measles vaccination at this visit. This vaccine is known to prevent pneumonia that could lead to death and brain swelling that could lead to seizures or deafness?”
  - “Definitely not”
  - “Probably not”
  - “Unsure”
  - “Yes”
- “Would you give your child the measles immunization at this visit. This immunization is known to prevent pneumonia that could lead to death and brain swelling that could lead to seizures or deafness?”
  - “Definitely not”
  - “Probably not”
  - “Unsure”
  - “Yes”
- “Would you give your child the measles shot at this visit. This shot is known to prevent pneumonia that could lead to death and brain swelling that could lead to seizures or deafness?”
  - “Definitely not”
  - “Probably not”
  - “Unsure”
  - “Yes”
- “Would you give your child the measles medicine at this visit. This medicine is known to prevent pneumonia that could lead to death and brain swelling that could lead to seizures or deafness?”
  - “Definitely not”
  - “Probably not”
  - “Unsure”
  - “Yes”

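### The measles status that defines the Aim 1 group and gates Aim 2 randomisation is guardian-reported with no verification described, although the medical record number is collected with consent

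*Protocol*

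**What the plan says.** - **Source of status.** The data list in section D includes "parental report of immunization status". No record-based status is listed.
- **Gate to the belief survey.** Section B, repeated in section C, sends on "All participants who identify that their child is under-immunized for measles". This is defined as a missed first MMR dose at 1 year or a missed second dose at 4 years.
- **Gate to randomisation.** Section B, Aim 2: "All guardians who complete the comprehensive survey will be randomized to receive one of four patient-centered immunization messages".
- **Item behind the gate.** The listed brief survey asks "Is your child up to date with all routine (Not including influenza, COVID-19, RSV) immunizations at this time", and then about influenza, COVID-19 and RSV. It lists no MMR or measles question.
- **Outcome.** Section D: "Our primary outcome is the demographic variables and immunization beliefs that are associated with RSV under-immunization". Aim 1 and the gate in section B concern measles.
- **Record access.** Under the recruitment heading in section C, the research assistant reviews the "ED electronic health record (dashboard or face sheet) and record (on a redcap database") five kinds of item: race/ethnicity, gender, triage (ESI) level, insurance status and chief complaints. The same section provides for "consent for collection of their name, medical record number, and survey responses".
- **Link to identity.** Section G keeps name and medical record number in a separate master key, to be destroyed once data collection closes and an adjudication process, not further described, is complete.

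**The concern.** One guardian-reported status does two jobs. It is the dependent variable for the Aim 1 associations, and it is the only route into Aim 2. To report it correctly, a guardian must know how many MMR doses the child has had and whether each was due, yet the listed survey asks only about routine immunisations as a whole.

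Where most children are up to date, even a small rate of false reports among them makes up a sizeable share of the reported cases. That pulls the Aim 1 associations towards the null if the error is unrelated to the factors studied. If accuracy differs by education or income, both of which section D names as stratifiers, the associations can be distorted in either direction.

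This is a matter of data collection. Dose dates that were never recorded cannot be brought back by a later analysis plan, and once the master key is gone the link needed to look them up is gone too.

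**Working it through.** The enrolment of about 800 is stated without a rate, effect size, alpha or power, so there is no calculation to reproduce. The check asks how large the misclassification could be.

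**Inputs from the protocol**
- N = 800 (Sample Size Considerations).
- True under-immunisation p = 8% to 20% (section A; childhood immunisations generally, not measles).

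**Assumptions, not in the protocol**
- Sensitivity Se of guardian report 80-95% and specificity Sp 90-98%.
- A binary factor present in 50% of families, with a true odds ratio (OR) of 2.0.
- Error unrelated to that factor.

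**Step 1: who passes the gate**

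True cases reported = N × p × Se. False cases reported = N × (1 − p) × (1 − Sp). Share truly under-immunised = true / (true + false).

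Central example, Se 90%, Sp 95%:
- p = 8%: true = 800 × 0.08 × 0.90 = 57.6; false = 800 × 0.92 × 0.05 = 36.8; total 94.4; share 57.6 / 94.4 = 61%.
- p = 20%: true = 800 × 0.20 × 0.90 = 144; false = 800 × 0.80 × 0.05 = 32; total 176; share 144 / 176 = 82%.

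Extremes of the assumed range:
- Lowest (p = 8%, Se 80%, Sp 90%): 51.2 / (51.2 + 73.6) = 41%.
- Highest (p = 20%, Se 95%, Sp 98%): 152 / (152 + 12.8) = 92%.

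Cases missed = N × p × (1 − Se): from 800 × 0.08 × 0.05 = 3.2 to 800 × 0.20 × 0.20 = 32. These guardians never reach the belief survey or randomisation.

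**Step 2: what happens to an association**

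The true risks p0 (factor absent) and p1 (factor present) must average p and give OR 2.0. This yields 5.53% and 10.47% at p = 8%, and 14.57% and 25.43% at p = 20%. Each observed risk is a = risk × Se + (1 − risk) × (1 − Sp).

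| p | Se | Sp | observed a0 | observed a1 | observed OR |
|---|---|---|---|---|---|
| 8% | 90% | 95% | 9.70% | 13.90% | 1.50 |
| 20% | 90% | 95% | 17.38% | 26.62% | 1.72 |
| 8% | 80% | 90% | 13.87% | 17.33% | 1.30 |
| 20% | 95% | 98% | 15.55% | 25.65% | 1.87 |

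The last two rows are the extremes, so an OR of 2.0 would appear as about 1.3 to 1.9.

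**Step 3: Aim 2**

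The gate comes before randomisation, so wrongly admitted families are allocated by chance across the four messages. The comparison between messages stays valid for those randomised. What changes is who they are: some have a child who is already up to date.

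**The case against.** The case against is substantial, and much of it stands.

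- A reader might infer that measles under-immunisation is itself the primary outcome. Section D does not say so: it makes the associated factors the outcome, and it names RSV. The RSV and measles passages have to be reconciled first. Section D gives parental report as the source of immunisation status without separating the two.
- A reader might infer that status provably rests on guardian memory alone. The protocol speaks of report, points to a data collection form that is not shown, and mentions an adjudication process without saying what is adjudicated. The supportable statement is that no verification is described.
- A reader might infer that dose dates are just one more field in the chart review already planned. That review is confined to the dashboard or face sheet, where nothing says vaccine dates appear. The consent as described covers name, record number and survey answers. A look-up through the record number needs the consent to be widened.
- The reference list includes a study of how accurately vaccination status is assessed in the emergency department. Only its title is available, and a title does not show that guardian report is inaccurate. It carries no weight here.
- The accuracy figures are assumed, and 41-92% is a wide range. It shows how large the problem could be, not how large it is.
- A reader might infer that the Aim 2 comparison is biased. Step 3 of the working shows that it is not.
- A record has its own errors, and keeping report for routing leaves the gate as it is. Both are true, and they limit the remedy to a sensitivity analysis. The dose dates must still be collected during the study for that analysis to be possible.

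**Conclusion.** The point holds in a limited form. The status that defines the Aim 1 group and admits guardians to Aim 2 is guardian-reported, with no verification described and no MMR item in the listed survey, while the record number that would allow a check is already collected with consent.

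Under the assumptions above, between about two in five and nine in ten reported cases would be genuine, and a doubling of odds would be seen as an odds ratio of about 1.3 to 1.9. These sizes depend on the assumed accuracy, on a general rather than measles-specific rate, and on error unrelated to the factor. If accuracy differs by education or income, the direction of bias in Aim 1 cannot be predicted. In Aim 2 the consequence is confined to whom the result describes.

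Reliance on guardian report is openly stated and is a legitimate choice for a survey. This is therefore a cheap improvement and not a flaw that invalidates the design. The mismatch between RSV and measles, however, has to be resolved whatever is decided about verification.

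**What to change.** 1. Reconcile section D with Aim 1 and the gate, so that one disease is named throughout.
2. Add an MMR item to the brief survey that asks about dose 1 and dose 2, so that the gate has a defined question behind it.
3. Extend the consent to the child's immunisation record. For consenting participants, have the research assistant use the medical record number to enter MMR dose 1 and dose 2 dates, or a code for not in the record, before the master key is destroyed.
4. Keep guardian report for routing. As sensitivity analyses, repeat the Aim 1 association analysis with record-based status in all participants, so that missed cases are corrected as well as false ones, and repeat the Aim 2 analysis in children whose under-immunisation the record confirms. For the belief items, the record can reclassify only those who were routed to the comprehensive survey, because missed cases never answer them.
5. Report agreement between guardian report and record.

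The cost is a consent line, a few REDCap fields and some research assistant time per participant, with no extra staff or clinical procedure. The main drawback is incomplete records: an absent entry does not prove that a child is unvaccinated. The record-based results should therefore stand beside the report-based ones and not replace them.

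### The only primary outcome names RSV under-immunization in a measles study, and correcting the word alone leaves the beliefs half with no comparison group

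*Protocol*

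**What the plan says.** The single primary outcome is in Protocol section D (Data Analysis): "Our primary outcome is the demographic variables and immunization beliefs that are associated with RSV under-immunization".

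Section B (Study Design) sets Aim 1 as "Identify the characteristics of the measles under-immunized population". The brief survey goes to all consenting guardians. Its status questions include "Is your child up to date with all routine (Not including influenza, COVID-19, RSV) immunizations at this time" and "Is your child immunized against RSV for this season". The longer survey on beliefs goes to a subset: "All participants who identify that their child is under-immunized for measles", defined by a missed first or second MMR dose. Section C repeats that restriction. Those who finish the longer survey are randomized to one of four messages.

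Before the message, the intent question is "Do you plan to get your child fully immunized for measles". After it, the Aim 2 narrative in sections B and C says guardians are "asked again if they plan to immunize their child against RSV this season", and also whether they would accept immunization at the current visit. The printed items that follow are all about measles. The first begins "Would you give your child the measles vaccination at this visit", and the other three change only the noun. The secondary outcome in section D is conversion from any lesser intent to intent, by message.

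**The concern.** The primary outcome and the design name different vaccines. This would not fail visibly. RSV status is on the brief survey, so cross-tabulating it against demographics, and against beliefs where they exist, would give results that look like a primary analysis. Those results would not describe the measles under-immunized population.

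The obvious one-word correction exposes a second problem. The outcome has two parts, demographics and beliefs, and they are collected from different sets of people. Demographics come from everyone. Beliefs come only from families already classed as measles under-immunized. An association between a belief and measles under-immunization needs belief data from families on both sides of that classification.

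In Aim 2, the narrative's RSV re-ask conflicts with the measles baseline and the measles scripts, so the text does not settle which post-message answer defines conversion, the endpoint of the randomized comparison.

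**Working it through.** **1. Which vaccine each element names**

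| Element | Protocol section | Vaccine |
|---|---|---|
| Study purpose | A | Measles |
| Aim 1 | B | Measles |
| Gate to beliefs survey, and through it to randomization | B, C | Measles |
| Baseline intent item | B | Measles |
| Four scripted post-message items | B | Measles (4 of 4) |
| Narrative of the post-message question | B, C | RSV |
| Primary outcome | D | RSV |

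RSV stands in three places where measles is meant: the Aim 2 narrative in B, its repeat in C, and the primary outcome in D. Enrolment itself depends on age and ED presentation, not on either vaccine.

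**2. Whether an RSV outcome is defined.** Measles under-immunization is defined by MMR doses in sections B and C. RSV under-immunization is defined nowhere. The RSV item asks about the current season, but its two affirmative answers refer to maternal immunization in pregnancy or immunization in infancy, while enrolled children are 1 to 6 years old. An analyst would have to invent the classification.

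**3. Who supplies which data.** Inputs: about 800 enrolled (section D, Sample Size Considerations) and an under-immunization range of 8-20% (section A). That range is for US childhood immunizations generally; applying it to measles at this site is an assumption. The protocol gives no inputs for the 800, so there is no calculation of its own to reproduce.

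- Belief respondents: 800 × 0.08 = 64; 800 × 0.20 = 160.
- No belief data: 800 − 64 = 736; 800 − 160 = 640.
- Per message arm if split equally: 64 / 4 = 16; 160 / 4 = 40.

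**4. What can be estimated once the outcome reads measles**

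| Component | Under-immunized | Immunized | Association estimable? |
|---|---|---|---|
| Demographics | 64-160 | 736-640 | Yes |
| Beliefs | 64-160 | 0 | No |

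Measles status is constant among belief respondents, so an odds ratio or difference by status does not exist for any belief item. The zero follows from the gate and does not depend on the 8-20% assumption.

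**5. What happens if RSV is kept.** RSV status can vary among belief respondents, but only within the measles under-immunized subgroup. That comparison does not answer Aim 1.

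**6. Measles status on the brief survey.** The listed items are caregiver age, child age, race, ethnicity, education, income, information source, social media time, routine immunizations, influenza, COVID-19 and RSV: 12 in all. One asks RSV status; none asks measles or MMR status specifically.

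**7. Conversion in Aim 2.** Conversion needs a before and an after on the same question. The baseline intent item is measles. The brief survey asks RSV status but not RSV intent, so an RSV re-ask has no baseline. The measles baseline and the scripted measles items share one four-level response scale, so conversion can be computed only from them. They are still different questions: one asks about plans for full immunization, the other about accepting it at this visit.

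**The case against.** The disease contradiction itself is hard to dispute. The case against what is built on it runs as follows.

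- **Measles status may be captured elsewhere.** The listed questions need not be the whole form, section C refers to a data collection form that is not shown, and the gate cannot work unless measles status is elicited somewhere. This stands as a limit: the count of zero applies to the listed items only, and the remedy is to confirm the form. The conclusion on beliefs does not depend on it.
- **Aim 1 is descriptive.** Asking reasons only of under-immunized families is a coherent design, and associated need not mean a between-group test. That supports descriptive reporting as an acceptable repair. It does not rescue an outcome worded as beliefs associated with under-immunization, which the collected data cannot show.
- **Beliefs could be related to measles intent within the subgroup.** This is a useful extra analysis at no added burden, since every belief respondent answers the intent item. It answers a question about hesitancy and does not restore the stated association with immunization status.
- **The Aim 2 narrative already describes two post-message questions.** Replacing RSV with measles would restore a like-for-like repeat of the plan question beside the acceptance question. This is fair. What remains is which of the two defines conversion, a secondary-outcome detail that an SAP may settle. The main point does not rest on it.

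**Conclusion.** The concern holds and must be fixed. The sole primary outcome names the wrong vaccine, and followed as written it leaves Aim 1 unanswered. After the word is corrected, the demographic part works, with about 64 against 736 to 160 against 640 families under the assumed 8-20% rate. The beliefs part has 0 comparators at any rate and any sample size. An SAP cannot repair this, because the gap lies in who is asked; answers not collected in the ED cannot be recovered by analysis.

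Confidence is high. The contradiction and the missing comparison group rest on the protocol's text alone. Only the illustrative counts depend on applying the general 8-20% range to measles at this site. The absence of an MMR item is established for the listed questions only.

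**What to change.** 1. **Section D:** replace RSV under-immunization with measles under-immunization, as defined in sections B and C.
2. **Brief survey or data collection form:** confirm that measles (MMR) status is recorded for every child, and add one item if it is not.
3. **Beliefs, one decision:** either limit the association analysis to the brief-survey and chart variables available for all participating families and report beliefs descriptively in the measles under-immunized group, or give the belief items to measles-immunized families as well. Beliefs by measles intent can be added within the subgroup under either option.
4. **Aim 2 narrative in sections B and C:** replace the RSV re-ask with measles wording that matches the baseline and scripted items.
5. **Conversion:** state that it is computed from the measles items, and name the post-message item that defines it. Repeating the baseline plan question word for word gives the like-for-like pair; the answer about accepting at this visit can be reported beside it.

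The cost is wording in three sections, at most one status item, and one decision. Descriptive reporting of beliefs adds no burden for participants. Giving the belief items to everyone adds that survey for about 640-736 more guardians under the same assumption.

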### **Sample Size Considerations**

We plan to enroll ~800 patients at AMC.

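### The Aim 2 conversion outcome is valid but one-way: it cannot show a wording that lowers acceptance among randomized guardians who already answered 'Yes'

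*Protocol*

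**What the plan says.** - **Outcome.** Protocol section D calls the secondary outcome an improvement in confidence and defines it as a move from "definitely not intent, unsure about intent, or probably not intent" to intent, broken down by message. No other outcome in the protocol uses the post-message answer, and no denominator is named.
- **Who is randomized.** Section B: "All guardians who complete the comprehensive survey will be randomized to receive one of four patient-centered immunization messages". Section C repeats this. Entry to the comprehensive survey depends on the guardian reporting that the child is behind on measles vaccination; the intent answer plays no part.
- **Aim.** Section B states Aim 2 as: "Explore the impact of favorable immunization messaging on parental confidence in the measles in the under-immunized population".
- **Baseline item.** "Do you plan to get your child fully immunized for measles", with four answers from 'Definitely not' to 'Yes'.
- **Post-message items.** The text says guardians are "asked again if they plan to immunize their child against RSV this season and if they would accept the immunization" at the current visit. The only item printed, in four wordings, is of the form "Would you give your child the measles vaccination at this visit", with the same four answers.

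**The concern.** The messages differ in one noun (vaccination, immunization, shot, medicine), and comparing them is the protocol's only randomized comparison. A wording can act in two ways: it can win over guardians who were not at 'Yes', or it can put off guardians who were. The stated outcome registers only the first. Two wordings with equal conversion but different retention of willing guardians would be reported as equivalent, although the data to separate them are collected.

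Willing guardians of under-immunized children are possible by design. The baseline item offers 'Yes', and the belief survey asks about practical barriers as well as attitudes, for example "I do not have transportation to get my child to the" appointment. Such guardians belong to the population that Aim 2 names.

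**Working it through.** **Inputs from the protocol.** Four arms; planned enrolment, "We plan to enroll ~800 patients at AMC"; general childhood under-immunization of 8-20% (section A). The 800 comes with no error rate, power or effect size, so there is no calculation to reproduce, and the point does not depend on it.

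**Assumed inputs.** The general 8-20% applies to measles; allocation is equal; and values are chosen for y (baseline 'Yes' share), c (conversion among baseline non-'Yes') and r (retention among baseline 'Yes').

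**Randomized number.** 800 × 0.08 = 64 and 800 × 0.20 = 160, so 16 to 40 per arm.

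**Identity.** Post-message 'Yes' share = (1 − y)c + yr. The outcome in section D is c if the denominator is baseline non-'Yes' guardians, or (1 − y)c if it is everyone randomized. Neither contains r. With equal c and y balanced by randomization, the difference missed is y(r_A − r_B).

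**Illustration.** 40 per arm, 10 of them 'Yes' at baseline (y = 0.25), and 8 of 30 others converting in both arms:

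| | Wording A | Wording B |
|---|---|---|
| Conversion | 8/30 = 27% | 8/30 = 27% |
| Retained 'Yes' | 9/10 | 5/10 |
| Post-message 'Yes' | (8+9)/40 = 42.5% | (8+5)/40 = 32.5% |

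**Range of the missed difference.**
- Retention 90% v 50%: 0.15 × 0.40 = 6 points to 0.40 × 0.40 = 16 points.
- Retention 90% v 80%: 0.15 × 0.10 = 1.5 points to 0.40 × 0.10 = 4 points.

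**Which analysis has more power.** This was simulated with latent normal intent before and after the message (correlation 0.5 or 0.8), baseline 'Yes' of 15, 25 or 40%, and post-message cutpoints equal or 0.3 SD harder. That gives 12 scenarios per effect, with 1000 replicates each and permutation tests at 5% across the four arms. One arm carries the effect. Power in %, mean (range) at 160 and mean at 64:

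| Effect in one arm | Conversion, 160 | Adjusted 'Yes', 160 | Conversion / adjusted 'Yes', 64 |
|---|---|---|---|
| Half of the baseline 'Yes' who would stay are lost | 5 (4-6) | 15 (6-36) | 4 / 9 |
| All guardians 0.5 SD better | 34 (26-47) | 48 (34-61) | 15 / 20 |
| All guardians 0.5 SD worse | 13 (7-19) | 29 (12-51) | 6 / 13 |
| 70% of 'Unsure' moved to 'Yes' | 33 (26-42) | 43 (33-54) | 15 / 18 |
| 35% of baseline non-'Yes' who would not convert are moved to 'Yes' | 83 (45-100) | 67 (27-96) | 49 / 35 |

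Rejection with no effect at 160 was 3.8-5.7% for conversion and 4.1-6.1% for adjusted 'Yes'. In the first row conversion stays at its false-positive rate, as the identity requires. In the last row conversion is the better test in all 12 scenarios.

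**The case against.** The strongest reply is that nothing here is wrong. Section A frames the second aim around hesitancy and section D labels the outcome an improvement; a guardian already at 'Yes' has no room to improve. Baseline intent precedes randomization, so comparing conversion among baseline non-'Yes' guardians is unbiased, and it is the better test when only hesitant guardians respond. All of this stands, and it is why conversion should be kept.

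Three further objections also carry weight.

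- **Detectability.** The illustration would not reach significance. For 17/40 v 13/40 the pooled share is 30/80 = 0.375 and the standard error √(0.375 × 0.625 × 2/40) = 0.108, so z = 0.10/0.108 ≈ 0.92, p about 0.36. For 9/10 v 5/10 Fisher's exact p is about 0.14. The by-arm count would be mainly descriptive.
- **Change of question.** Baseline asks about a plan; the printed follow-up asks about this visit. A guardian who intends to vaccinate elsewhere may leave 'Yes' without being put off. The shift is common to all arms, so comparisons between wordings stand, but a single such move is not clean evidence of lost willingness.
- **SAP detail.** Supportive analyses are often left to a SAP, which is not shown. But the protocol itself fixes the outcome definition, and that definition is what leaves these guardians out.

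A reader might infer that a deterrent wording would go unnoticed altogether. The definition does not support that: deterrence among non-'Yes' guardians lowers conversion and is seen. Only loss among baseline-'Yes' guardians is invisible.

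**Conclusion.** The point holds as a gap in coverage. The outcome in section D cannot show a wording that lowers acceptance among guardians already willing, whichever denominator is used, although those guardians are randomized, re-asked and part of Aim 2's population. The missed difference is 6-16 points under 15-40% baseline 'Yes' and 90% v 50% retention, and 1.5-4 points under 90% v 80%. All these rates are assumptions.

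Two stronger readings are not supported. One is that many willing guardians are to be expected: the barrier items make them possible, but the protocol gives no share. The other is that the all-randomized 'Yes' share should replace conversion: which has more power depends on who responds, as the simulation shows.

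Section D also does not say which post-message item scores intent. That is a separate ambiguity and does not raise the weight of this point. For a secondary outcome under an exploratory aim, priority is low to moderate.

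**What to change.** In section D:

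1. Keep conversion as the defined outcome and name baseline non-'Yes' guardians as its denominator.
2. Add, as a supportive analysis, a comparison of the post-message 'Yes' share across the four arms in all randomized guardians, adjusted for the baseline answer.
3. Report 'Yes' to non-'Yes' moves by arm, descriptively.
4. State that the printed measles item about this visit scores post-message intent, and reconcile it with the RSV-worded repeat question in sections B and C.
5. State that only differences between arms are interpreted as message effects, not before-after change, because the two items ask different things.

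The cost is one more analysis and one table from answers already collected, with no added participants and no loss of the defined outcome. The supportive analysis would have low power to prove loss among willing guardians: at most 36% in the simulated scenarios at 160 randomized, and a mean of 9% at 64.
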